Protocol Title: User-Led Meaningful Activity and Early-Stage Dementia

Document Title: Study Protocol

NCT: NCT05159869

Document Date: 03DEC2021

Study Protocol

The clinical trial phase will be a pilot randomized, controlled trial exploring the design and feasibility of a novel approach to dementia intervention development. The randomized, controlled pilot study compares the efficacy of the co-creation of a tailored activity plan with a wait-list control group. Using a two-group randomized, parallel design, 60 persons with early-stage dementia will be assigned to treatment or wait-list control.

Recruitment: Potential participants will be recruited through 1) the Johns Hopkins University Maximizing Independence (MIND) at Home study, 2) the Johns Hopkins Bayview Medical Center Memory Clinic, 3) community-based social agencies such as the Alzheimer's Association, and 4) independent and semi-independent residences designed for older adults including continuing care retirement communities and assisted living facilities. Recruitment efforts are aimed at persons living with early-stage dementia and their informal/unpaid caregivers using three main forms of messaging: (a) flyers, (b) a description of the study that was prepared originally for clinicaltrials.gov, and (c) in-person recruitment presentations. All recruitment materials describe the general nature and goals of the research and provide information about what participation involves and monetary compensation. The Principal Investigator (PI) is listed as the source for additional information and addressing questions in all materials.

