Feedback Session: The potential participant and his/her caregiver will be provided with feedback from the neuropsychological assessment within one week of testing. If the results indicate that the potential participant is cognitively healthy, meets criteria for mild cognitive impairment, or meets criteria for dementia that has advanced beyond the early, or mild, stage, this will be the final session with the potential participant. If the results of the assessment indicate that the potential participant is indeed at a mild stage of dementia, he or she and the PI will work together in a subsequent session to co-design a meaningful activity plan and map out a gradation plan to correspond with

disease progression. The caregiver will be advised on how to modify/grade the activity(ies) as the disease advances.

Randomization and Study Arm Protocol: Persons randomized to the User-Led Meaningful Activity intervention group will begin the treatment protocol (described below) right after randomization. The intervention will consist of 2-3 sessions lasting 60-90 minutes each in which participants identify the basis/topic of the activity plan, receive dementia psychoeducation, and map out an activity gradation plan. There will be a check-in at 8 months. The neuropsychological battery that was administered at baseline will be re-administered 4 months and 12 months after baseline. Persons randomized to the wait-list control group will begin the treatment protocol after four months' time. There will be a check-in at 8 months. The neuropsychological battery that was administered at baseline will be administered 4 months and 12 months after baseline.

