Protocol Title: User-Led Meaningful Activity and Early-Stage Dementia

Document Title: Statistical Analysis Plan

NCT: NCT05159869

Document Date: 21AUG2025

Statistical Analysis Plan

The study followed a randomized, two-arm parallel design. Seventy (70) dyads comprising community-dwelling individuals with early-stage dementia and their primary caregivers were assigned to treatment or wait-list control. Treatment group participants received the co-designed meaningful activity intervention, and all dyads were reassessed at four months from baseline. After four months, wait-list control dyads received the same intervention and were retested four months later (i.e., eight months from baseline).

Analyses were based on the Intent-To-Treat (ITT) principle, including every patient who was randomized. All tests were performed at two-tailed significance $\alpha=0.05$. First, chi-squared and t-test tests were used to compare intervention and control dyads on baseline characteristics. The primary hypothesis held that a co-designed meaningful activity intervention would significantly decrease the frequency and intensity of neuropsychiatric symptoms (NPS) and slow cognitive decline across multiple domains (i.e., memory and learning, executive function, visuospatial abilities, attention, language, processing speed). The secondary hypothesis was that a co-designed meaningful activity intervention would significantly increase emotional well-being (e.g., reduce depression and anxiety) and strengthen self-identity. To test the hypotheses, main treatment effects at four months were examined using analysis of covariance (ANCOVA). Given prior research linking caregiver characteristics to ratings of neuropsychiatric and psychosocial outcomes, caregiver sex, race/ethnicity, education, and relationship to the person living with dementia (PLWD) were identified a priori as covariates. Standardized effect sizes (d) were calculated as the adjusted mean difference between groups divided by the square root of the model's mean square error (MSE).

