To evaluate whether wait-list control participants derived benefits comparable to those of the meaningful activity group after receiving the intervention, change scores were examined from 4 months (T2) to 8 months (T3) in the wait-list control group and compared with change scores from baseline (T1) to 4 months (T2) in the meaningful activity intervention group. Analyses were conducted using the same ANCOVA framework applied in the primary analysis. It was hypothesized that the magnitude of treatment effects would be similar across groups, reflecting replication of benefit, and therefore the between-group difference in change would not be statistically significant.

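### The wait-list replication analysis expects a non-significant difference as the sign of replicated benefit, but that result cannot tell full replication from no effect in either group

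*SAP*

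**What the plan says.** The final paragraph of the SAP gives its purpose as: "To evaluate whether wait-list control participants derived benefits comparable to those of the meaningful activity group after receiving the intervention". The wait-list change from T2 (4 months) to T3 (8 months) is set against the intervention-arm change from T1 (baseline) to T2, using the ANCOVA framework of the primary analysis. The SAP's general rule is two-sided testing at 0.05. The paragraph then hypothesizes effects of similar size in the two groups, "reflecting replication of benefit, and therefore the between-group difference in change would not be statistically significant".

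Nothing else is offered for judging comparability. The only effect measure elsewhere in the SAP is a point estimate: "Standardized effect sizes (d) were calculated as the adjusted mean difference between groups", scaled by the root mean square error, with no interval. The replication analysis is not made conditional on a positive four-month result. The protocol (Follow-Up Data Collection Periods) describes this part of the design as confirming gains in wait-listed participants, and it too gives no criterion.

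On what was measured at T3, the SAP says that "wait-list control dyads received the same intervention and were retested four months later (i.e., eight months from baseline"). For the wait-list group, the protocol (Randomization and Study Arm Protocol) says: "The neuropsychological battery that was administered at baseline will be administered 4 months and 12 months after baseline", with a check-in at month 8. Its Follow-Up Data Collection Periods section mentions an 8-month visit for that group but names no instruments.

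**The concern.** A two-sided test of a difference asks whether the data rule out equality. Failing to rule it out is not evidence of equality, and here equality would not be evidence of benefit either. Two equal improvements, two absent effects and two equal deteriorations all give a true difference of zero. When a real gap does exist, a smaller or noisier sample makes the predicted result more likely, so weaker data would favour the claim of replication.

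The comparison is also outside the randomization. Baseline to month 4 in one arm and month 4 to month 8 in the other differ in calendar time, disease stage and number of earlier assessments. In a progressive condition, untreated change need not be equal in the two windows. Practice effects add to this for any cognitive test repeated at month 8, and the documents leave unclear which tests those were.

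At stake is the SAP's own stated question. A report that follows the plan as written could claim replication from a result that carries almost no information about it.

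**Working it through.** The documents give no power, target effect, SD, margin, allocation ratio or dropout figure, so there is no plan figure to reproduce. The check is of how the planned comparison behaves.

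**Inputs**
- Two-sided α = 0.05 (SAP, second paragraph).
- "Seventy (70) dyads comprising community-dwelling individuals with early-stage dementia and their primary caregivers" (SAP). Assumed split equally: n = 35 per arm. The protocol planned 60, or 30 per arm.
- Assumed sensitivity case: 20% loss, n = 28 per arm.
- Assumed SD of change = 1, so all effects are in SD units; covariates are ignored.
- The effect sizes and the 0.2 SD drift difference are illustrations, not estimates for this trial.

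**What the test depends on.** Let μ be the untreated change in each window and θ the treatment effect. The net gap is δ = (μ₁ + θ₁) − (μ₂ + θ₂). With μ₁ = μ₂, δ = 0 whenever θ₁ = θ₂, whether both are large, zero or negative. The chance of p > 0.05 is then 95% at any sample size and any SD.

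**Chance of a non-significant result.** P = F(t; ν, λ) − F(−t; ν, λ), where F is the non-central t distribution function, ν = 2n − 2, t is the 0.975 quantile of central t, and λ = δ/√(2/n).
- n = 35: √(2/35) = 0.239, t = 1.995. For δ = 0.5, λ = 2.09 and P = 0.459.
- n = 28: √(2/28) = 0.267, t = 2.005. For δ = 0.5, λ = 1.87 and P = 0.549.

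| Case | Net gap δ | n = 35 | n = 28 |
|---|---|---|---|
| Full replication (0.5 and 0.5) | 0 | 95% | 95% |
| No effect in either group | 0 | 95% | 95% |
| Equal worsening (−0.5 and −0.5) | 0 | 95% | 95% |
| Half the benefit (0.5 and 0.25) | 0.25 | 82% | 85% |
| First arm 0.3, wait-list 0 | 0.3 | 76% | 80% |
| First arm 0.5, wait-list 0 | 0.5 | 46% | 55% |
| No effect, drift differs by 0.2 | 0.2 | 87% | 89% |
| 0.5 lost, 0.2 drift masks it | 0.5 − 0.2 = 0.3 | 76% | 80% |
| 0.5 lost, 0.2 drift adds to it | 0.5 + 0.2 = 0.7 | 18% | 27% |

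At 30 per arm, the 0.3 and 0.5 rows without drift are 79% and 52%.

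**Precision of what could be reported instead (95% half-widths)**
- Between-group difference, t·√(2/n): 1.995 × 0.239 = 0.48 at n = 35; 2.005 × 0.267 = 0.54 at n = 28.
- Wait-list group's own T2–T3 change, t/√n with n − 1 df: 2.032/√35 = 0.34 at n = 35; 2.052/√28 = 0.39 at n = 28.
- Wait-list treated change minus the same participants' untreated T1–T2 change: SD = √(2 − 2ρ). For an assumed correlation ρ of successive changes from 0 to −0.5, the SD is 1.41 to 1.73, giving 0.49 to 0.60 at n = 35.

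**Equivalence test (90% CI inside ±margin, true difference 0).** At n = 35 the expected 90% half-width is about 0.40. Power is about 0% at a margin of 0.3, 33% at 0.5, 60% at 0.6 and 90% at 0.8. At n = 28 it is about 0%, 17%, 43% and 81%.

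**The case against.** The best defence is that the SAP already tests for benefit where it should, in the randomized four-month ANCOVA. A clear positive result there would argue against no effect in either group, so the 95% against 95% comparison matters only if the replication result is read alone. That is right, and the primary analysis is not in question. But a positive primary result does not show that the wait-list group benefited. A first-arm gain of 0.5 SD that the wait-list fails to reproduce would still go undetected 46% of the time, and the SAP does not link the two analyses.

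Second, the paragraph records a hypothesis and not a decision rule. Also true, but it is the only criterion offered for the stated question, and the SAP itself ties non-significance to replication.

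Third, the wait-list change scores are to be examined, so group mean changes would ordinarily be available. This is fair: what is missing is a stated interval, test or requirement for that change, not necessarily the estimate.

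Fourth, the dropout and drift inputs are arbitrary. They are illustrations, and the central result needs neither. It needs only equal untreated change, and where that fails the comparison is harder to interpret.

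Fifth, a formal equivalence test is weak at this size and a margin set now would be late. Both stand, and they shape the fix. Low power is also a reason not to read p > 0.05 as comparability.

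Finally, the SAP's word for the month-8 assessment names no instruments, so the conflict with the protocol's battery schedule is one of unclear content. That point is secondary and the conclusion does not rest on it.

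**Conclusion.** The concern holds. Nothing the SAP states for this analysis can show comparable benefit, and its predicted result is equally likely under full replication, no effect and equal worsening (95% each, given equal untreated change). Under the assumed 35 per arm and SD of change of 1, it also occurs 46% of the time when a 0.5 SD effect is wholly lost in the wait-list group, and 76% when a 0.3 SD effect is lost (55% and 80% at 28 per arm). A 95% interval of about ±0.48 SD leaves most plausible losses of effect unresolved. The fault is in the follow-on analysis of a pilot trial. It should be fixed, but it does not touch the randomized four-month comparison.

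**What to change.** 1. Stop using non-significance as the sign of replication. Suggested wording: *The difference between the wait-list T2–T3 change and the intervention-arm T1–T2 change is reported with its 95% CI for each outcome. It is descriptive, and p > 0.05 is not interpreted as comparable benefit.* If the recorded hypothesis is to be kept for the record, add this as an explicit reporting caveat. Claim comparability only if the 90% CI lies inside a justified margin, labelled post hoc if outcomes have been seen; otherwise report it as inconclusive.
2. Report the wait-list group's own T2–T3 change, and its contrast with the same participants' untreated T1–T2 change, each with a 95% CI, as supportive evidence only.
3. State that both contrasts are non-randomized and open to practice and progression effects.
4. State which instruments were given at month 8, reconcile the SAP with the protocol's battery schedule, and limit the analysis to outcomes measured at T3.

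The cost is wording, intervals and one extra contrast on data already collected. The gain is limited. The SAP is dated August 2025 and written in the past tense, so a margin set now would probably be post hoc, and equivalence would often be inconclusive at this size. The within-wait-list contrast is no more precise than the between-group one. The main benefit is the interval and the descriptive label.
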